## 9.2.6.1 ABPM substudy

This substudy is designed for a non-inferiority assessment in systolic blood pressure from Screening (Visit 1) to Day 270 (Visit 6) between obicetrapib and placebo. The non-inferiority margin was selected in accordance with the United States FDA guidelines (Assessment of Pressor Effects of Drugs, Guidance for Industry). The non-inferiority margin was chosen to assess if obicetrapib is not substantially inferior to placebo for elevations in systolic blood pressure. The assumption for the common standard deviation is determined by a literature review and the obicetrapib Phase 2 program. From the reference paper by Vollmer et al, the estimate of the standard deviation for the change in systolic blood pressure (mmHg) for hypertensive participants based on 24-hour ABPM measurements was 8.0 (95% confidence interval: 6.9, 9.4).

A subset of approximately 200 participants from selected study sites who consent to participate will be enrolled in the ABPM substudy. For inclusion in the substudy analysis, participants must have an acceptable 24-hour ABPM data collection at Screening (Visit 1), as defined in a separate study manual. This sample size will allow for non-inferiority to be established between the obicetrapib group compared to the placebo group, with desired power of >80%, against a non-inferiority difference of 3 mmHg. This assumes a mean treatment difference of 0 mmHg for the obicetrapib group compared to the placebo group, with a standard deviation of 8 mmHg, at a 1-sided significance level of 0.05.

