A substudy is designed for a non-inferiority assessment in systolic blood pressure from Screening (Visit 1) to Day 270 (Visit 6) between obicetrapib and placebo. The non-inferiority margin was selected in accordance with the United States Food and Drug Administration guidelines (Assessment of Pressor Effects of Drugs, Guidance for Industry) [1]. The non-inferiority margin was chosen to assess if obicetrapib is not substantially inferior to placebo for elevations in systolic blood pressure. The assumption for the common standard deviation is determined by a literature review and the obicetrapib Phase 2 program. From the reference paper by Vollmer et al, the estimate of the standard deviation for the change in systolic blood pressure (mmHg) for hypertensive participants based on 24-hour ABPM measurements was 8.0 (95% confidence interval: 6.9, 9.4) [2].

A subset of approximately 200 participants from selected study sites who consent to participate will be enrolled in the ABPM substudy. For inclusion in the substudy analysis, participants must have an acceptable 24-hour ABPM data collection at Screening (Visit 1), as defined in a separate study manual. This sample size will allow for non-inferiority to be established between the obicetrapib group compared to the placebo group, with desired power of >80%, against a non-inferiority difference of 3 mmHg. This assumes a mean treatment difference of 0 mmHg for the obicetrapib group compared to the placebo group, with a standard deviation of 8 mmHg, at a 1-sided significance level of 0.05.

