3.2.2 The Full Analysis Set (FAS)

The FAS will include all participants who are randomized into the study, take any study drug, and have at least 1 post-treatment lipid data assessment. Treatment classification will be based on the randomized treatment.

3.2.3 *Modified Intent-to-Treat (mITT) Population*

The mITT Population will include all randomized participants who receive at least 1 dose of any study drug and have data for both the Day 1 and Day 84 LDL-C assessments. Treatment classification will be based on the randomized treatment.

3.2.4 *Modified Intent-to-Treat (mITT) On-Treatment Population*

The mITT On-Treatment Population will include all randomized participants who, have data for both the Day 1 and Day 84 LDL-C assessments. Participants in the obicetrapib group with PK values less than 3 standard deviations from the mean obicetrapib concentration should be excluded. Treatment classification will be based on the randomized treatment.

Rationale: in previous studies, such as ROSE (protocol number TA-8995-201) and TULIP (protocol number TA-8995-03), and ROSE2 (protocol number TA-8995-202), it was demonstrated that the minimally observed obicetrapib concentration for C_{max} was less than three standard deviations from the mean at respectively Week 4 and Week 12 [3-5].

3.2.5 *Per-Protocol (PP) Population*

The PP Population will include all participants in the mITT Population who did not experience a major protocol deviation that potentially impacted the primary efficacy endpoint. The PP Population, along with the reason for exclusion, will be finalized prior to study unblinding.

3.2.6 *Safety Population*

The Safety Population will include all participants who receive at least 1 dose of any study drug. Treatment classification will be based on the actual treatment received. The Safety Population will be the primary population used for the safety analyses.

3.2.7 *24-hours ABPM Population*

The 24-hour ABPM Population will include all participants in the ITT Population who received at least 1 dose of any study drug and have valid data for both the baseline and Day 270 24-hour ABPM assessments and have 80% to 120% treatment compliance.

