 - ≥ 100 mmHg
 - ≥ 110 mmHg
 - change from baseline by ≥ 15 mmHg.

The change in average 24-hour SBP from Baseline to Day 270 will be analyzed using an ANCOVA model with a fixed effect for the treatment group and covariates of Baseline average SBP, Age, Sex and background diagnosis of hypertension. The change in average 24-hour SBP from Baseline to Day 270 will be presented by treatment group with a 2-sided 95% CI (1-sided $\alpha = 0.025$) for the difference between the treatment groups. Obicetrapib will be considered non-inferior to placebo if the upper bound of the 2-sided 95% CI (1-sided $\alpha = 0.025$) for the difference between the treatment groups is less than the non-inferiority margin corresponding to 3 mmHg.

The model will be fit assuming unequal variances for each treatment group. The primary analysis will be conducted based on the 24-hour ABPM Population.

A sensitivity analysis will be performed using all randomized participants from ITT Population who received at least 1 dose of study drug and had either a Baseline or Day 270 ABPM assessment. If the participant only had an assessment at one of these two visits, the value at the missing visit will be imputed. Similarly, if a participant had an invalid ABPM assessment (following the definition of a valid ABPM assessment described previously), the records at that visit will be set to missing and the overall assessment value will be imputed. Missing data will be imputed based on multiple imputation methodology assuming the data are MAR. The variables for the imputation model will consist of the SBP values from Baseline and Day 270, along with treatment group, Age, Sex and background diagnosis of hypertension. For the imputation methodology, 100 imputed data sets will be generated with no missing values at Day 270. For each imputation data set, the change from baseline to Day 270 will be analyzed using the ANCOVA model described above. The results of these 100 analyses will be combined to construct the treatment estimates using the parameter

estimates and associated standard errors. Similarly, the difference of the adjusted treatment means (obicetrapib vs. placebo) will be presented with the associated standard error and two-sided 95% confidence interval. Randomly chosen seed numbers will be selected for the analysis and will be retained. The sample SAS code can be found in [Appendix D](#).

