6 CHANGES FROM PROTOCOL-SPECIFIED STATISTICAL ANALYSES

There have been three changes from the protocol v6.0.

The first change is the addition of time points to the exploratory endpoint, Day 84 and Day 180, to evaluate trough levels of obicetrapib from Baseline.

The second change relates to the effect of obicetrapib on cardiovascular events. Additional exploratory endpoints were added:

- The time from Randomization until the first confirmed occurrence of a composite of CV death, non-fatal MI, or non-fatal stroke, or coronary revascularization
- The time from Randomization until the first confirmed occurrence of a composite of CHD death, non-fatal MI, or non-fatal stroke, or non-elective coronary revascularization
- The time from Randomization until the first confirmed occurrence of a composite of CHD death, non-fatal MI, or non-fatal stroke, or coronary revascularization
- The time from Randomization until the first confirmed occurrence of a composite of CHD death, non-fatal MI, or non-fatal stroke
- MALE events
- Number of total CV events.

The third change is the inclusion of subgroup analysis.

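### The ABPM substudy is sized at 1-sided 0.05 but decided at 1-sided 0.025; on the plan's own inputs the power is about 70%, not above 80%

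*SAP*

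**What the plan says.** **Sizing.** Protocol 9.2.6.1 and SAP 2.2.2 give the same justification for about 200 participants: "with desired power of >80%, against a non-inferiority difference of 3 mmHg", "with a standard deviation of 8 mmHg, at a 1-sided significance level of 0.05". The assumed true effect is nil: "This assumes a mean treatment difference of 0 mmHg for the obicetrapib group compared to the placebo group". The SD comes from a cited study whose estimate "based on 24-hour ABPM measurements was 8.0 (95% confidence interval: 6.9, 9.4"). The only condition the sizing text sets for entering the substudy analysis is an acceptable Screening recording. It states no allowance for loss, no covariate gain and no substudy allocation ratio; the main trial randomizes 2:1.

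**Decision rule.** SAP 3.5.7 reads: "Obicetrapib will be considered non-inferior to placebo if the upper bound of the 2-sided 95% CI" for the treatment difference "is less than the non-inferiority margin corresponding to 3 mmHg". It labels that interval as 1-sided 0.025 twice, and the code in SAP Appendix D requests two-sided limits at alpha 0.05, which agrees. SAP 3.1.6 states the hypotheses and the 3 mmHg margin but no alpha.

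**Analysis set.** SAP 3.2.7 limits the primary ABPM analysis to dosed ITT participants who "have valid data for both the baseline and Day 270 24-hour ABPM assessments and have 80% to 120% treatment compliance".

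**Record of changes.** SAP section 6 opens: "There have been three changes from the protocol v6.0". It then lists PK time points, cardiovascular endpoints and subgroup analyses.

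**The concern.** The SAP carries two alphas for one test. The power statement uses the looser, and the pass/fail rule uses the stricter. The sizing has almost no reserve even at the looser level, so moving to 0.025 takes it well below its stated target before anyone is lost.

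SAP 3.5 says no inference will be applied to safety endpoints, yet 24-hour systolic pressure is the one safety endpoint for which SAP 3.1.6 states a hypothesis test. If the bound crosses 3 mmHg, a reader who relies on a power above 80% may take the result as a pressor signal when the substudy was simply too small for the test applied.

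**Working it through.** **Inputs.** Margin 3 mmHg, true difference 0, SD of change 8 mmHg, N about 200 (Protocol 9.2.6.1, SAP 2.2.2). Allocation 2:1 is carried over from the main randomization (SAP 2.2.1).

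**Formulas.** At 2:1, SE = SD × √(4.5/N). Power = Φ(3/SE − z), with z = 1.645 at 1-sided 0.05 and 1.960 at 0.025.

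**1. Reproduce the stated figure.** SE = 8 × √(1/133.3 + 1/66.7) = 1.20, so 3/SE = 2.50.
- At 0.05: Φ(2.50 − 1.645) = 80.4% (noncentral t: 80.1%).
- N for 80%: (1.645 + 0.8416)² × 64 × 4.5/9 = 197.8, or 198 as 66 + 132.

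The plan's claim reproduces almost exactly, which supports reading it as 2:1, unadjusted and without loss.

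**2. Apply the actual rule.**
- At 0.025: Φ(2.50 − 1.960) = 70.5% (noncentral t: 70.1%).
- N for 80%: (1.960 + 0.8416)² × 64 × 4.5/9 = 251.2, or 252 as 84 + 168.

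**3. Loss and covariate gain, all at 1-sided 0.025.** The documents give no ABPM loss rate; 5% is the main trial's dropout assumption, and 10% and 20% are my assumptions. They also give no correlation ρ between Baseline and Day 270, so 0.5 to 0.8 is assumed. With equal variance at both visits, adjusting for baseline gives a residual SD of 8 × √((1 + ρ)/2): 6.93 at ρ = 0.5 and 7.59 at ρ = 0.8.

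| Analysed | Unadjusted SD 8 | ANCOVA, ρ = 0.8 | ANCOVA, ρ = 0.5 |
|---|---|---|---|
| 200 (no loss) | 70.5% | 75.0% | 82.3% |
| 190 (5%) | 68.3% | 72.9% | 80.3% |
| 180 (10%) | 66.0% | 70.5% | 78.2% |
| 160 (20%) | 60.9% | 65.4% | 73.3% |

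**4. Break-even for 80% at 0.025.** Residual SD = 3/(2.8016 × √(4.5/N)); ρ = 2 × (SD/8)² − 1.
- N = 200: SD at most 7.14, ρ at most 0.59.
- N = 180: SD at most 6.77, ρ at most 0.43.
- N = 160: SD at most 6.39, ρ at most 0.27.

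With 200 analysed, covariates must therefore explain 1 − (7.14/8)² = 20% of the variance of the change.

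**5. SD uncertainty.** Over the cited interval, unadjusted with 200 analysed, power at 0.025 is 82.6% at SD 6.9 (SE 1.035) and 56.7% at SD 9.4 (SE 1.41).

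**The case against.** The strongest reply is that 70.5% is not the power of the planned test either. SAP 3.5.7 specifies an ANCOVA on baseline systolic pressure, age, sex and hypertension. With all 200 analysed, a correlation of 0.59 or lower would restore 80%, and the other covariates could add something. That stands: how far true power falls short depends on inputs the documents do not give. It does not rescue the stated figure, which was computed on an SD of 8 at a different alpha and claims no covariate gain.

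Three further points have some force.
- The 2:1 ratio within the substudy is inferred. It fits the stated figure, however, and 1:1 with 200 analysed would give SE 1.13 and 75.5% at 0.025, still below 80%.
- The protocol defines no ABPM model or ABPM population, so the SAP might be read as filling a gap rather than changing anything. But Protocol 9.2.6.1 does state a significance level for establishing non-inferiority and a condition for inclusion in the analysis, and the SAP departs from both. The SAP also disagrees with itself (2.2.2 against 3.5.7).
- Part of the SAP's revision table is not visible in the public copy, so the point about recording extends only to section 6.

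Finally, the stricter rule protects against a false claim of non-inferiority, and the multiple-imputation sensitivity analysis keeps more participants. Both are true, and they limit the severity.

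**Conclusion.** The point holds and should be fixed. The stated power does not describe the test that will decide non-inferiority. With SD 8, 2:1 allocation, no true effect and 200 analysed, a drug that does not raise blood pressure would miss the criterion about 29% of the time, where both documents imply under 20%. Losses under SAP 3.2.7 would make this worse and a covariate gain would make it better; over the assumed ranges in the table, power runs from about 61% to 82%. The estimate, interval, margin and type I error are unaffected.

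**What to change.** - **Keep the SAP 3.5.7 criterion** (upper bound of the 2-sided 95% CI below 3 mmHg). It is the stricter of the two, and the Appendix D code already uses it.
- **Restate the power** in Protocol 9.2.6.1 and SAP 2.2.2 at 1-sided 0.025 for the 24-hour ABPM Population. Give the allocation ratio, the SD, the assumed loss and any assumed covariate gain. On the unadjusted SD of 8 with 200 analysable the figure is about 70%, and about 68% if the trial's own 5% dropout applies. Any higher figure should name the residual SD or correlation behind it.
- **Add to SAP section 6** both the difference in alpha and the definition of the 24-hour ABPM Population.

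The cost is wording in two documents and a less favourable power statement. No participants are added and the decision rule does not change.

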4 DATA SAFETY MONITORING BOARD

An independent Data Safety Monitoring Board (DSMB) will monitor unblinded safety data, including blood pressure changes over time and the occurrence of ESIs during the study on a bi-annual basis (ie, approximately every 6 months). Subjects, investigators, site staff and in general all personnel directly involved in the conduct of the study will remain blinded to the participants' treatment assignment until the completion of the study.

Details related to the DSMB responsibilities, authorities, and procedures will be documented in a DSMB Charter.

5 ANALYSIS TIMING

5.1 Interim Analysis

No interim analysis is planned.

5.2 Pre-Final Analysis

After the database is locked and exclusions from analysis populations have been finalized, the randomized treatment assignments will be unblinded and the pre-final analysis will be generated. Pre-final tables, figures, and listings (TFLs) will be provided approximately 3 weeks after database lock.

5.3 Final Analysis

After all comments on the pre-final analysis have been resolved and the study database is declared final, the final analysis will be generated. If there were no changes to the pre-final analysis or the study database, the pre-final TFLs may be considered final. In addition to TFLs, SDTM data and ADaM data along with associated files will be provided. Associated files may include annotated case report forms (CRFs), SDTM specifications, SDTM programs, ADaM

specifications, ADaM programs, TFL programs, and CDISC Define packages for both SDTM and ADaM data.

6 CHANGES FROM PROTOCOL-SPECIFIED STATISTICAL ANALYSES

There have been three changes from the protocol v6.0.

The first change is the addition of time points to the exploratory endpoint, Day 84 and Day 180, to evaluate trough levels of obicetrapib from Baseline.

The second change relates to the effect of obicetrapib on cardiovascular events. Additional exploratory endpoints were added:

- The time from Randomization until the first confirmed occurrence of a composite of CV death, non-fatal MI, or non-fatal stroke, or coronary revascularization
- The time from Randomization until the first confirmed occurrence of a composite of CHD death, non-fatal MI, or non-fatal stroke, or non-elective coronary revascularization
- The time from Randomization until the first confirmed occurrence of a composite of CHD death, non-fatal MI, or non-fatal stroke, or coronary revascularization
- The time from Randomization until the first confirmed occurrence of a composite of CHD death, non-fatal MI, or non-fatal stroke
- MALE events
- Number of total CV events.

The third change is the inclusion of subgroup analysis.

7 PROGRAMMING SPECIFICATIONS

Analyses will be performed using SAS® version 9.4 or higher. All available data will be presented in subject data listings which will be sorted by subject and visit date as applicable. Detailed Programming Specifications will be provided in a separate document.

APPENDIX B: PREFERRED TERMS FOR HYPERTENSION

Preferred Term
Accelerated hypertension
Blood pressure ambulatory increased
Blood pressure diastolic increased
Blood pressure inadequately controlled
Blood pressure increased
Blood pressure orthostatic increased
Blood pressure systolic increased
Diastolic hypertension
Essential hypertension
Hypertension
Malignant hypertension
Mean arterial pressure increased
Systolic hypertension
Blood pressure abnormal
Blood pressure ambulatory abnormal
Blood pressure diastolic abnormal
Blood pressure orthostatic abnormal
Blood pressure systolic abnormal
Labile blood pressure
Hypertensive crisis
Hypertensive emergency
Hypertensive urgency
Orthostatic hypertension

APPENDIX C: PREFERRED TERMS FOR AAA AND CAROTID REVASCULARIZATION

Preferred Term for AAA	Preferred Term for carotid revascularization
Acute aortic syndrome	Carotid angioplasty
Aortic aneurysm	Carotid artery bypass
Aortic aneurysm repair	Carotid artery stent insertion
Aortic aneurysm rupture	Carotid artery stent removal
Aortic aneurysm syphilitic	Carotid endarterectomy
Aortic dilatation	Carotid revascularisation
Aortic dissection	
Aortic dissection rupture	
Aortic intramural haematoma	
False lumen dilatation of aortic dissection	
Penetrating aortic ulcer	

APPENDIX D: SAS EXAMPLE CODE 24 HOUR ABPM ANALYSIS

ANCOVA ANALYSIS

Note:

TREATMENT = 0 (Placebo), 1 (Obicetrapib)
BASE = Baseline average SBP 24-hour ABPM value
CHG = Change from Baseline at Day 270
AGE = Age
SEX = Sex
HP = Background diagnosis of hypertension

```
proc mixed data=SBP_24HR;  
  class TREATMENT SEX HP;  
  model CHG = TREATMENT BASE AGE SEX HP / ddfm=satterth solution cl;  
  lsmeans TREATMENT /diffs cl alpha=0.05;  
run;
```

SENSITIVITY ANALYSIS

1. Missing data will be imputed 100 times to generate 100 datasets. Multiple imputation will be performed in two steps:

- 1.1 Non-monotone values will be imputed to create a monotone missing pattern.

Note:

TREATMENT = 0 (Placebo), 1 (Obicetrapib)
BASE = Baseline average SBP 24-hour ABPM value
Day270 = Day 270 average SBP 24-hour ABPM value
AGE = Age
SEX = Sex
HP = Background diagnosis of hypertension

```
proc mi data=SBP_24HR seed=63974 n impute=100 out= SBP_24HR_imp1;  
  class TREATMENT;  
  mcmc impute=monotone;  
  var BASE DAY270;  
run;
```

- 1.2 The remaining monotone missing values will be imputed.

```
proc sort data= SBP_24HR_imp1; by _Imputation_;run;

proc mi data=SBP_24HR_imp1 n impute=1 out= SBP_24HR_imp2;
  by _Imputation_;
  class TREATMENT SEX HP;
  var TREATMENT SEX HP BASE DAY270;
  monotone reg(BASE= TREATMENT SEX HP);
  monotone reg(DAY270= TREATMENT SEX HP BASE);
run;
*****
```

2. For each imputed dataset, the percent change from baseline to Day 270 will be analyzed using Ancova model.

```
*****
```

Note:

TREATMENT = 0 (Placebo), 1 (Obicetrapib)
BASE = Baseline average SBP 24-hour ABPM value
CHG = Change from Baseline at Day 270
AGE = Age
SEX = Sex
HP = Background diagnosis of hypertension

```
*****
```

```
proc mixed data= SBP_24HR_imp2;
  by _Imputation_;
  class TREATMENT SEX HP;
  model CHG = TREATMENT BASE AGE SEX HP / ddfm=satterth solution cl;
  lsmeans TREATMENT /diffs cl alpha=0.05;
run;
*****
```

3. The parameter estimates will be combined using Rubin's method.

```
*****
```

Note: MI Analyze to combine imputations

```
*****
```

```
proc mianalyze parms(classvar=full)=mixLSM;
  class TREATMENT;
  modeleffects TREATMENT;
  ods output parameterestimates=mi_LSM;
run;
```

```
proc mianalyze parms(classvar=full)=mixDIFF;
  class TREATMENT;
  modeleffects TREATMENT;
  ods output parameterestimates=minus_mi_DIFF;
run;
*****
```

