BASE = Baseline LDL_C value

PCHG = Percent change from Baseline to Day 84

```
CVRISK = 1 (HeFH), 0 (non-HeFH)
STATIN = 1 (HIS), 0 (non-HIS)
*****
proc mixed data= TEMP;
  by _imputation_;
  class TREATMENT CVRISK STATIN;
  model PCHG = TREATMENT BASE CVRISK STATIN /ddfm=satterth solution cl;
  repeated / group=TREATMENT;
  lsmeans TREATMENT / cl diff;
run;
*****
1.3
*****
Note: MI Analyze to combine imputations.
*****
proc mianalyze parms(classvar=full)=mixLSM;
  class TREATMENT;
  modeleffects TREATMENT;
  ods output parameterestimates=mi_LSM;
run;
proc mianalyze parms(classvar=full)=mixDIFF;
  class TREATMENT;
  modeleffects TREATMENT;
  ods output parameterestimates=minus_mi_DIFF;
run;
*****
```

Sensitivity Analyses

The first sensitivity analysis will be performed imputing missing LDL-C values at Day 84 based on the assumption the data are MNAR using a control-based pattern mixture method. At Day 84, the data will be split into two groups as follows: (1) all participants randomized to the obicetrapib treatment group that had a non-missing value at Day 84; and (2) either participants randomized to the placebo treatment group, or participants that had a missing value at Day 84. For the second group, 100 data sets will be imputed. The variables for the imputation model will consist of the LDL-C values from Baseline and Day 84, along with CV risk (HeFH or non-HeFH) and Baseline statin therapy (HIS or non-HIS). In this manner, missing data at the Day 84 assessment will be estimated from the placebo treatment group. Each data set will be combined with the first group to obtain 100 imputed data sets with no missing values at Day 84. For each imputation data set, the percent change from baseline to Day 84 will be analyzed using the ANCOVA model described above. The results of these 100 analyses will be combined to construct the treatment estimates using the parameter estimates and associated standard errors. Similarly, the difference of the adjusted treatment means (obicetrapib vs. placebo) will be presented with the associated standard error and two-sided 95% confidence interval. Randomly chosen seed numbers will be selected for the analysis and will be retained.

The second sensitivity analysis will be performed using a tipping point approach in the following steps [6-7]. The same analysis method as specified for primary analysis will be applied when analyzing adjusted data generated under each plausible shift parameter:

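### The Appendix D example code for the ABPM analysis contradicts the SAP 3.5.7 text: pooled variance in both models, and listed variables missing from the sensitivity-analysis imputation

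*SAP*

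**What the plan says.** **Text, SAP 3.5.7.** Change in 24-hour systolic pressure from Baseline to Day 270 is analysed by ANCOVA with treatment, baseline pressure, age, sex and hypertension diagnosis. On variance: "The model will be fit assuming unequal variances for each treatment group". Non-inferiority is declared if the upper limit of the two-sided 95% interval lies below 3 mmHg. The primary analysis uses the 24-hour ABPM Population, which SAP 3.2.7 restricts to participants with valid recordings at both visits.

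Imputation belongs to a separate analysis: "A sensitivity analysis will be performed using all randomized participants from ITT Population who received at least 1 dose of study drug", with at least one of the two recordings. Its imputation model contains the Baseline and Day 270 pressures, "along with treatment group, Age, Sex and background diagnosis of hypertension". The section then points to Appendix D for sample code.

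**Code, SAP Appendix D.** The primary ANCOVA and the post-imputation ANCOVA share the statement "model CHG = TREATMENT BASE AGE SEX HP / ddfm=satterth solution cl". Neither call has a REPEATED statement. Imputation step 1.1 (MCMC) has "var BASE DAY270". Step 1.2 has "var TREATMENT SEX HP BASE DAY270", and its Day 270 regression is "monotone reg(DAY270= TREATMENT SEX HP BASE".

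**For contrast, SAP 3.4.1.** The LDL-C text asks for the same unequal variances, and its code supplies them with "repeated / group=TREATMENT".

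**The concern.** SAP 3.5 applies no inference to safety endpoints in general. The ABPM comparison is the exception, with hypotheses in SAP 3.1.6 and a decision rule in 3.5.7. That rule compares a confidence limit with 3 mmHg, so it depends directly on the standard error. Text and code give different standard errors whenever the arm SDs differ, and 2:1 allocation is what makes the difference matter. The SAP does not say which of the two prevails. A programmer who follows Appendix D would run a different test from one who follows section 3.5.7.

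The imputation mismatch is a lesser matter. It bears on how far the sensitivity analysis can be trusted as a check on the primary result, not on the primary result itself.

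**Working it through.** **The plan's own power figure.** Inputs from SAP 2.2.2: about 200 participants, margin 3, SD 8, true difference 0, one-sided 0.05. Allocation 2:1 is from SAP 2.2.1.
- SE = 8 × √(1/133.3 + 1/66.7) = 1.20.
- Power = Φ(3/1.20 − 1.645) = Φ(0.855) = 80.4%. The stated power above 80% reproduces, under a common SD.

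**Part 1: variance (primary test and post-imputation model).** Without a REPEATED statement with a GROUP option, PROC MIXED fits one residual variance. The Satterthwaite option sets the degrees of freedom and does not separate the variances.

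The illustration assumes n₁ = 133 (obicetrapib), n₀ = 67 (placebo) and one-sided 0.025. The documents give no arm-specific SDs. The values below are assumptions taken from the cited estimate of one SD, 8.0 (95% interval 6.9 to 9.4).

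- True SE = √(s₁²/n₁ + s₀²/n₀)
- Pooled SE = √{[(n₁−1)s₁² + (n₀−1)s₀²]/(n₁+n₀−2) × (1/n₁ + 1/n₀)}
- Type I error at the margin = Φ(−1.96 × pooled SE / true SE)

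For s₁ = 6.9 and s₀ = 9.4:
- True SE = √(47.61/133 + 88.36/67) = √1.677 = 1.295.
- Pooled variance = (132 × 47.61 + 66 × 88.36)/198 = 61.19.
- Pooled SE = √(61.19 × 0.02244) = 1.172.
- Ratio 0.905, so type I error = Φ(−1.774) = 3.8%.

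| Obicetrapib SD | Placebo SD | Pooled/true SE | Type I error, pooled |
|---|---|---|---|
| 8 | 8 | 1.000 | 2.5% |
| 8 | 9.4 | 0.948 | 3.2% |
| 6.9 | 9.4 | 0.905 | 3.8% |
| 8 | 6.9 | 1.050 | 2.0% |
| 9.4 | 6.9 | 1.105 | 1.5% |

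Simulation (40,000 trials per setting) agrees. With SDs 6.9/9.4, type I error is 3.9% pooled and 2.6% with unequal variances. With 9.4/6.9 it is 1.6% and 2.5%, and power at a true difference of 0 is 65% pooled against 72%.

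The result hardly depends on total size. At exactly 2:1 the squared SE ratio is approximately (2s₁² + s₀²)/(s₁² + 2s₀²). For 6.9/9.4 this is 183.58/224.33 = 0.818, whose root is 0.905 again. At 1:1 it would be 1 whatever the SDs.

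**Part 2: imputation (sensitivity analysis only).**

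| Variable listed in 3.5.7 | Step 1.1 | Step 1.2 |
|---|---|---|
| Baseline and Day 270 pressure | yes | yes |
| Treatment | no (in CLASS, not in VAR) | yes |
| Sex | no | yes |
| Hypertension | no | yes |
| Age | no | no |

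Step 1.1 fills a missing Baseline when Day 270 is present. With the arms pooled, a Day 270 value raised by treatment is read partly as a raised Baseline, so the change is understated. Step 1.2 fills a missing Day 270 and does include treatment.

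Illustration, assuming a between-person SD of 12, SD of change 8, 10% of Day 270 values missing and a true difference of 3.0 mmHg:

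| Baselines missing | Estimate, step 1.1 without treatment |
|---|---|
| 2% | 2.97 |
| 5% | 2.90 |
| 10% | 2.80 |
| 20% | 2.62 |

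With treatment included, the estimates are about 2.96 to 3.02. With no Baseline missing, or with a true difference of 0, there is no bias beyond simulation noise.

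**The case against.** The strongest reply is that Appendix D is labelled as example code and that SAP section 7 defers detailed programming specifications to another document. The SAP also abbreviates code elsewhere: in 3.4.3 the Poisson text names CV risk and statin covariates, but its code has treatment alone. A reader might infer that the trial will use a pooled variance. The documents do not show that; they show two specifications of one analysis. What remains is that section 3.5.7 sends the reader to this code and no precedence rule exists.

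A reader might also infer that the imputation faults tilt the formal non-inferiority decision. They cannot. The primary population requires both valid recordings, so nothing is imputed there. Nor is treatment absent from imputation throughout, only from step 1.1. An acceptable Screening recording is a condition of entry, so step 1.1 should seldom act. It is not ruled out, because section 3.5.7 admits participants with either recording and sets invalid recordings to missing. For the age omission, no material effect on the treatment difference has been shown.

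Finally, 6.9 and 9.4 are confidence limits for a single SD, and the sizing assumes a common SD. Placing opposite limits in opposite arms is a constructed case. This objection stands: the figures illustrate sensitivity and do not predict an error rate.

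**Conclusion.** The mismatch between text and code is real and should be reconciled. It has two parts of different weight.

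The missing variance statement affects the primary non-inferiority test and the post-imputation model. Its effect is nil if the arm SDs are equal. Over the assumed SD combinations above, one-sided type I error runs from about 1.5% to 3.8% against 2.5%. The direction depends on which arm varies more, and the documents do not indicate which.

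The imputation omissions affect the sensitivity analysis alone and should matter little. Where step 1.1 acts on a real pressor difference, it shrinks that difference, which is the direction that favours non-inferiority.

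This is not evidence that the wrong test will be run. It is an ambiguity in the one formal safety test, and it is best settled before unblinding.

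**What to change.** 1. Add "repeated / group=TREATMENT" to both PROC MIXED calls in Appendix D, as in the LDL-C code.
2. Replace steps 1.1 and 1.2 with a fully conditional specification (FCS) regression that includes TREATMENT, AGE, SEX, HP, BASE and DAY270. Alternatively, run the MCMC step by treatment with AGE and numerically coded SEX and HP in its VAR statement, and add AGE to the VAR and monotone regression statements of step 1.2. Running step 1.1 by treatment without those additions would still leave age, sex and hypertension out.
3. State that the section 3.5.7 text prevails over example code.
4. In the same edit, correct the Appendix D step 2 description, which speaks of percent change although the model analyses CHG, the change in mmHg.

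The cost is a few lines and one sentence. No new data, sample size change or design change is needed, and the result is what section 3.5.7 already specifies.
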